3.0 Study Objectives and Design

3.1 Study Objectives

To answer the following research questions:

Primary Objectives and endpoints (for detailed summaries of the outcomes, see section 3.3)

- 1) *Does regular consumption of white potatoes increase sleep quality, measurable as the ratio of total sleep time to time in bed: "sleep efficiency (SE)"?*
- 2) *Does regular consumption of white potatoes improve night-time glycaemic control compared with other, less nutrient dense starchy staples (white pasta, white rice etc.)?*

Secondary Objectives and endpoints

- 3) *Does regular consumption of white potatoes improve endothelial function?*
- 4) *Does regular consumption of white potatoes improve autonomic function?*
- 5) *Does regular consumption of white potatoes improve blood lipid profiles, and glucose control (fasting glucose, fasting insulin, glycated haemoglobin), when compared with other, less nutrient dense starchy staples?*
- 6) *Does regular consumption of white potatoes improve blood pressure?*

3.2 Intervention overview

Table 1. Summary of the Starchy Study's arms and Interventions, as written on ClinicalTrials.Gov

Arms	Assigned Interventions
Experimental: Habitual potato consumption At least 230g of white potatoes, including fresh and frozen, baked, boiled, and mashed potatoes, will be consumed in the evening meal, in replacement of non-nutrient-dense starchy staples, for 12 weeks.	Dietary Supplement: Habitual potato consumption Potatoes are to be consumed in the evening meal, every evening for 12-weeks.
Active Comparator: Habitual non-nutrient-dense staple consumption Isocaloric amounts of non-nutrient-dense starchy staples, such as white rice, white pasta, and white couscous, will be consumed in the evening meal for 12 weeks.	Dietary Supplement: Habitual non-nutrient-dense staple consumption White rice, white pasta or white couscous are to be consumed in the evening meal, every evening for 12-weeks.

Dietary Intervention

The intervention (potato group) will consume 230 g white potatoes as one of their 5-a-day fruits and vegetables, providing ~1000 mg potassium (enough to increase national median intakes up to

recommended intakes) in their evening meal (25% of energy intake from carbohydrates, or 12.5% of total energy intake, including fresh and frozen baked, boiled, mashed potato products), whereas the control group will consume isoenergetic amounts of non-nutrient dense starchy staples (white pasta, white rice, or couscous).

Participants will be given £5 per week, in renumeration for the purchasing of the starchy component.

Although participants cannot be blinded to what they're consuming, they will be blinded to whether they are in the control or the intervention group, to reduce risks of bias.

We have chosen not to adjust for % estimated energy requirements as potatoes are typically eaten as a standard portion size (e.g., standard baked potato is ~200g), and this simplifies the intervention for the participant.

Participants will be required to source the potatoes and make these meals themselves, however, they will be provided with rotating 4-weekly recipe cards, with instructions on how to prepare meals. Guidance on eating out will be provided to maintain study compliance, as successfully utilized in other studies (29). We believe this will sufficiently standardise nutrient intakes from the non-starchy staple dietary components both inter and intra arms. We plan to use the dietary recalls at weeks 2, 4 and 8 to reinforce dietary advice, and to make adaptations to rotating menus based on individual needs, if participants are struggling with adherence (30).

Recipes will be generated by modelling meals in Nutritics software and will aim to follow food based dietary guidelines for the UK (31) and the US (32).

Printed leaflets and dietetic/nutrition led coaching will be used to advise individuals on how to incorporate potatoes into their evening meal (to be eaten before 8pm) to ensure that the diet contains a mixed composition of potato categories, with consideration for habitual dietary intakes, as used in our previous dietary intervention studies (26,40). The study duration of 12 weeks has been selected as sufficient time to induce changes in fasting FMD (41), and glycaemic control (42). A parallel arm has been chosen to maintain compliance due to the duration of the intervention.

Dietary Advice (Week 2 dietary consultation).

Both arms will receive food-based dietary advice from an associate nutritionist, broadly consistent with UK dietary guidelines and USDA recommendations.

These recommendations will be inclusive of, but not limited to:

- Discourage snacking before bed and encourage food consumption before 8pm, to prevent unfavourable postprandial glycaemic responses as observed in clinical trials (33), and other metabolic dysfunction biomarkers (34), explained by chrono-nutrition (35). Although individuals tend to consume dinner later than at usual at the weekend (36), most of the UK and US population eat between 18:00-20:00 (37, 38), therefore we believe this is a feasible ask.
- Reduce excessive alcohol intake or excessive changes in exercise habits.
- To consume similar levels of salt, types of fat, and added sugars, to standardise across arms.
- Additionally, participants will receive personalised advice on front of package labelling, eating out and choosing convenience meals.

Compliance

Biochemical Assessment

Compliance will be monitored by 24 h urinary potassium excretion, which is shown to recover 75% of potassium intake (39). These samples will be analysed by flame photometry (40). No other appropriate biomarkers of compliance are specific enough to monitor differences in the control and potato interventions in this study design. Additionally, sodium excretion will be analysed to indicate dietary sodium intake. This is a relevant indicator in our study as sodium intake could confound the results of this study.

Urinary creatinine will be used as one marker to distinguish between complete and incomplete 24 h urine collections (41), specifically the Knuiman et al creatinine excretion method (urinary creatinine [mmol/d] \times 113)/(21 \times body weight [kg]) (42), which has been shown to be the most sensitive and specific (43). Samples with a creatinine index <0.7 will be discarded as incomplete.

Additionally, self-reported missing samples (more than a few drops, as assessed by word of mouth and urine collection forms) and samples with a total volume <400 mL will be marked as incomplete, as outlined in the NHANES survey (44).

Midline urine samples will be analysed within a week of collection, to assess compliance.

Dietary Assessment

Dietary assessment evaluations will be built into the study design to evaluate and encourage compliance to treatments, including 4-d food records (WK 0, 6, 12), and 24h dietary recalls (WK 2, 4, 8) with the multipass method (45).

Additionally, self-reported compliance methods will be employed via an evening meal checklist in the data diaries provided to participants. This will determine the level of compliance (%) and may be used as stratum in analysis. $\geq 75\%$ of overall days exposed to the starch, as well as 75% of the days exposed in the final four weeks, will be counted as compliant. Any rates below 75% in either of these time periods, will be counted as non-compliant for ITT.

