Endpoints	
Primary
 
 • 7-day Sleep efficiency, at baseline and endline • 12-day nocturnal mean glucose (using Continuous Glucose Monitors (CGM) during sleep), at baseline (0 weeks) and endline (12 weeks) 
Secondary
 
 • Endothelium-dependent vasodilation (measured by ultrasound image analysis as Flow-Mediated Dilation (FMD)), at baseline and endline. • 12-day daytime and 24-hour glucose metabolism (CGM outcomes, glycaemic variability, time in range). • 48hrs nocturnal, daytime and stress-related heart rate variability (measure of autonomic function; higher range the more autonomic function) • 12-week daytime and night-time continuous blood pressure (Aktiia blood pressure bracelet) • Blood parameters 
 ◦ Glucose control (fasting HbA1C, fasting glucose and insulin) ◦ Lipids • Body composition 
 ◦ weight and waist circumference ◦ % body fat and lean body mass (Tanita scales) • Visual Analogue Scale (VAS) assessments of satiety, included in 4-day diet diaries. • Urinary potassium and sodium • Urinary alkaloids (calystegines) 
Compliance
 
 • Urinary potassium and sodium • Dietary assessments 
 ◦ 24-hour recall (Wk 2, 4, 8) ◦ 4-day food diary (Wk 0, 6, 12) ◦ Self-reported adherence: checklist of evening meal
Main Inclusion Criteria	Participants will be healthy male or females, aged between 40-80 years who consume ≤4 fruits and vegetables a day (excluding potatoes), with a less favourable sleep efficiency score of <85%

Statistical Methodology and Analysis	
Differences between groups (minimized for age, gender, BMI) will be analysed using Linear mixed models for outcomes with 3 timepoints (urinary outcomes, dietary intake data), with change being the dependent factor, participant ID as random effect, treatment and season as fixed effects, and baseline outcome and BMI as covariates. Variables with 2 timepoints will be assessed with an ANCOVA regression model.
 
A 2 -sided P value <0.05 will be considered as showing statistical significance.
 
For more details of statistical analysis plan, see section 4.2.

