4.2 Study statistical plan

Mean differences between groups will be assessed at endpoint, adjusting for baseline values and other potential other covariates (maximum 3, as per the rule of 1 covariate per 10 participants).

For the outcomes with 3 timepoints (urinary Na, K, Na:K and calystegines), this will be assessed using a using Linear mixed models (mixed command) with change being the dependent factor, participant ID as random effect, treatment and season as fixed effects, and baseline outcome as a covariate. Variables with 2 timepoints (all other outcomes) will be assessed with an ANCOVA regression model (regress command), with baseline as a covariate. BMI, sex and age may also be covariates depending on the balancing of the arms. Sex differences will also be explored in some outcomes with known sexual dimorphisms, with the use of a sex interaction term.

A 2 -sided P value <0.05 will be considered as showing statistical significance.

Normality will be assessed visually with histogram and Q-Q plot of residuals, and heteroscedasticity with a fitted-residual plot, to satisfy the model assumptions.

We will primarily analyse outcomes on an intention-to-treat basis, analysing participants as randomised. Per-protocol analyses—restricted to participants meeting prespecified adherence criteria—will be performed to assess robustness.

All statistics will be run on Stata/MP 18.0.

[figure not shown]

Figure 5. Flow chart of the recruitment procedures

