5.4 Randomisation Procedures

Participants will be randomised to either the intervention or control arm, with an allocation ratio of 1:1. A minimisation procedure will be used that considers gender, age, ethnicity, BMI) in the randomization, by using the Shiny App software, which can be accessed at:

https://fsella.shinyapps.io/VM_app/?_ga=2.186170153.125318758.1628174827-961835063.1626383516 (71).

Screening data will be entered into minimisation software, by the research lead (See randomisation SOP). This database will balance the treatment arms for the following variables:

1. *Gender*. 2 groups: Male; Female
2. *Age*. 2 groups: 40-59; 60-80 y
3. *BMI*. 2 groups: Healthy weight 18.5-24.9; Overweight-Obese ≥ 25

Randomisation codes will be generated by the software and recorded on the relevant documentation in the Case Report Form and enrolment log. The randomization protocol follows the same protocol as used previously by our group for a parallel, two-arm, randomized controlled trial (30) for which a study statistician was employed. It has not been deemed necessary to employ a study statistician on the current trial due to the similarity of the study design, but the protocol will be discussed with a statistician from the King's Joint Clinical Trials Unit.

Participants will be blinded to whether they are receiving the intervention or the control, but it is not possible to blind them to the food itself. Also, as the study team is limited by resources, observer blinding is also impossible; however, the researcher undertaking statistical analysis will be blinded prior to analysis using a second set of study ID codes. FMD analysis will be conducted through semi-automated software analyses, which will reduce bias.

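### The single creatinine bar for 24 h urine (14.7 mg/kg/day for everyone) may selectively discard complete collections, and no analysis without that exclusion is planned

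*Combined protocol and SAP*

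**What the plan says.** Section 3.2 (Compliance, Biochemical Assessment) makes 24 h urinary potassium the biochemical check of compliance. It introduces the completeness test with "Urinary creatinine will be used as one marker to distinguish between complete and incomplete 24 h urine collections". The index is creatinine in mmol/day times 113, divided by 21 times body weight in kg. The method is supported by a citation and the remark "which has been shown to be the most sensitive and specific", without figures. The consequence is stated flatly: "Samples with a creatinine index <0.7 will be discarded as incomplete". Two further criteria follow: self-reported missed voids, and "samples with a total volume <400 mL will be marked as incomplete".

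The Synopsis describes the population thus: "Participants will be healthy male or females, aged between 40-80 years". Section 3.8 excludes BMI below 18.5 or above 35.

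The Synopsis lists urinary potassium, sodium and calystegines among the secondary endpoints. Section 3.3 calls calystegines an exploratory biomarker and names urinary potassium as a possible stratifier. Section 4.2 specifies the model: "For the outcomes with 3 timepoints (urinary Na, K, Na:K and calystegines") are analysed by a linear mixed model of change, with the baseline value as covariate.

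The plan gives no expected discard rate, repeat collection, missing-data method for discarded urine, or analysis without the index exclusion.

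**The concern.** A completeness test should respond to how much urine was missed. This one also responds to how much creatinine a person makes per kg of total body weight, because the expected output is one constant with no term for sex, age or body composition. Anyone whose true output lies below the bar will tend to fail even with a perfect collection. The missed-void and volume criteria cannot rescue such a sample, since they only add reasons to mark one incomplete.

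Three things are at stake. First, Section 4.2 models change from baseline, so a discarded baseline sample removes the participant from that analysis. Second, if low output per kg goes with age, sex or body fat, the urinary results would describe a selected part of the randomised population. Third, the whole sample is discarded, so Na:K is lost too, although a shortfall in volume scales sodium and potassium together and largely cancels in the ratio.

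**Working it through.** **Inputs from the documents.** Constants 113 and 21 and cut-off 0.7 (Section 3.2); ages 40-80 and BMI 18.5-35 (Section 3.8); 80 recruited and 68 completing (Section 4.1; 80 x 0.85 = 68 reproduces). There is no planned discard rate to reproduce.

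**Inputs assumed.** Creatinine output per kg, its variation, and the sex and age mix.

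**1. The bar.** 0.7 x 21 = 14.7 mg/kg/day, or 14.7/113 = 0.130 mmol/kg/day, for everyone.

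**2. How complete a collection must be to pass.** This is 14.7 divided by true output:

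| True output (mg/kg/day) | Completeness needed |
|---|---|
| 21 | 70% |
| 18 | 82% |
| 16 | 92% |
| 15 | 98% |
| 14 | 105% (a complete collection fails) |

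The test therefore has a different tolerance for different people.

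**3. Scaling with weight.** At 1.65 m, BMI 25 is 68.1 kg and needs 68.1 x 0.130 = 8.9 mmol/day; BMI 35 is 95.3 kg and needs 12.4 mmol/day, a ratio of 35/25 = 1.40. A collection with 10 mmol scores 1130/(21 x 60) = 0.90 at 60 kg and 1130/(21 x 90) = 0.60 at 90 kg, crossing 0.70 at 1130/14.7 = 76.9 kg. The 60 and 90 kg comparison holds creatinine fixed, so it shows how the formula behaves. It does not show that heavier participants fail more often.

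**4. Chance that a complete sample is discarded.** Phi((14.7 - mu)/(CV x mu)) for assumed mean mu, with CV from 10% to 25%:

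| mu (mg/kg/day) | P(discard) |
|---|---|
| 21 | 0.1% to 11.5% |
| 18 | 3% to 23% |
| 16 | 21% to 37% |
| 15 | 42% to 47% |
| 14 | 58% to 69% |
| 12 | 82% to 99% |

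**5. Illustrative population, every collection complete.** Assumed: mean output (28 - 0.2 x age) mg/kg/day in men and 85% of that in women; age uniform 40-80; half women; between-person CV 12-15%; within-person CV 10-15%; three samples each. There is no weight or BMI term. The average index reaches 0.70 at (28 - 14.7)/0.2 = 66.5 years in men and (28 - 14.7/0.85)/0.2 = 53.5 years in women. A completer counts as usable with baseline plus at least one later sample, which is what the Section 4.2 model requires. The SE ratio is 1/sqrt(usable/68); it ignores the smaller loss from having only one later sample.

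| Assumed output | Samples discarded | Usable of 68 | SE ratio |
|---|---|---|---|
| As stated (mean 14.8) | 53-54% | 27-29 | 1.53-1.59 |
| 20% higher | 24-29% | 45-49 | about 1.2 |
| 30% higher (mean 19.2) | 15-20% | not needed here | not needed here |
| Mean raised to 21 | 8-12% | not needed here | not needed here |

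Discards among women aged 60 and over are 85-90% in the first row, about 60% with output 20% higher and 42-46% with output 30% higher; among men under 60 in the first row they are 13-21%. The age and sex pattern follows from the assumed formula; the documents do not report it.

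**The case against.** The protocol cites a published method and says it performed best. That source cannot be checked here, and it may be a good reason to keep the index. The remark comes with no figures, however, and nothing in the text shows that the cut-off was tested at ages 40-80 with BMI up to 35. Creatinine is also described as only one marker among several, but an index below 0.7 is enough on its own for discard.

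The strongest objection concerns size. The documents give no creatinine output by sex, age or body fat, and the first row of the illustration has a mean of 14.8, almost exactly on the bar, so a loss near one half follows from that choice. This stands. The loss is a range.

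A reader might go further in four ways, none of which the documents support.

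- *That the rule does discard complete samples from older, female and heavier participants.* This needs output norms that are not given, and the weight effect was not simulated.
- *That compliance cannot be verified in older women.* Compliant status is set by the evening-meal checklist (Section 3.2). Dietary recalls, meal photographs (Section 9.6) and serum potassium (Section 3.3) do not depend on urine completeness.
- *That the treatment comparison is biased.* Minimisation on gender, age ("Age*. 2 groups: 40-59; 60-80 y") and BMI in Section 5.4 should make losses similar between arms. Any upward selection of retained samples acts alike at each timepoint, so it should largely cancel in change from baseline.
- *That the main result is at risk.* Neither primary endpoint uses urine, and the sample size in Section 4.1 does not depend on this rule.

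**Conclusion.** The concern holds in a limited form. From the documents alone, the bar is 14.7 mg/kg/day for everyone, the index by itself triggers discard, a person with true output of 14 mg/kg/day fails with an average complete collection, and no rescue or alternative analysis is planned. It follows that the rule may selectively remove complete collections from people with low creatinine output per kg. That these are older participants and women, and possibly those with more body fat, is an assumption.

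Under the assumptions shown, the loss of complete samples runs from about 8-12% (mean 21 mg/kg/day) to about 53%, where the standard error is about 1.5-1.6 times larger. The consequence is reduced precision and a less representative set for urinary potassium, sodium, Na:K and calystegines, and a thinner biochemical check of compliance. Discarding Na:K on this index is hard to justify whatever the true norms are.

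**What to change.** In Sections 3.2 and 4.2, before unblinding:

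1. Treat an index below 0.7 as a flag instead of grounds for automatic discard.
2. Do not apply the index exclusion to Na:K.
3. Prespecify that 24 h potassium, sodium and calystegines are analysed both with and without samples that fail only on the index. Keep the missed-void and under-400 mL exclusions in both analyses.
4. Report samples failing the index by sex, age group, BMI and arm.

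This keeps the cited index and needs no replacement equation. The cost is a paragraph of text and one extra run of the urinary models, on data already collected. The downside is that some truly incomplete collections enter one of the two analyses and add noise to 24 h totals, and Na:K from a partial collection may carry some time-of-day variation.

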5.4 Schedule of Treatment for each visit

Details of screening methods are summarized in Section 5.3

NB: All times allocated are estimates. Although the study team endeavours to keep within the limits of these suggestions, there may be deviations due to unprecedented circumstances or varying participant needs.

1st contact: Email exchange, online.

Upon responding to advertisements, volunteers will be emailed a participant information sheet, and an electronic questionnaire (via Qualtrics software). All forms will be reviewed by a study team member and will be assessed against inclusion/exclusion criteria. Participants will be informed the outcome at the earliest opportunity. If eligible, participants will then be invited to attend an introductory call.

2nd contact: Introductory call. Location, online, to be held at the discretion of the volunteer. 15-30 minutes.

All eligible participants will receive a telephone/video call (depending on the participant's preference) with a member of the study team, both to introduce themselves and the study. The information sheet will be discussed, and the consent form will be introduced. This call will serve as a chance for participants to ask questions and have their understanding of the study checked before giving

consent. This call also allows the study team to build rapport with participants. After this call, a consent form (online form), will be emailed out, and upon return, they will be invited to a virtual 1:1 run-in induction.

Once consent is obtained, participants will be posted a '**study pack**' consisting of:

1. Participant information guide
2. Study diary for writing data (sleep, BP, weight, evening meal compliance checklist)
3. Recipes
4. Equipment
 - a. CGM (primary outcome)
 - b. Motion Watch (primary outcome)
 - c. Aktiia blood pressure bracelet (secondary outcome)
 - d. 24-hour urine collection kits (X3) (adherence)
 - e. Kitchen Scales (to weigh 24hr urine at midline)
 - f. Bathroom scales (only if participant does not own any, secondary outcome)
5. Equipment leaflets, including SOPs with photos for guidance.
6. 4-day food diary incl VAS for appetite (X3)
7. Packaging to post equipment/diaries

3rd contact: Virtual (or in-person) run-in. Location at the discretion of the volunteer. 60 minutes.

Before this session, volunteers will be given leaflets and videos on the equipment they will apply and/or measure to give them a good understanding.

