This follow-up session will be an overview and a chance for participants to ask outstanding questions. This will ensure that the study lead is happy that participants have suitable understanding of the process and are happy to continue with the process.

A summary of the training needs that will be addressed are written below:

Self-taken measurements include:

1. Body weight with home scales (Weekly, from wks.0 - 12)

Need to apply the following equipment alone:

1. Motion watch (7days)
2. Aktiia bracelet (7 days)
3. CGM (12 days)

Participants will be made aware that they are able to contact the study team at any time when they need. The contact details (study email and phone number) will be provided in the participant information guides they receive along with their equipment, as well as on email invitations.

4th contact: Clinic visit 1 (Wk 0), MRU at KCL. ~130 minutes.

The study team will have correspondence with participants to arrange a suitable date for their baseline clinic visit.

Participants will attend the MRU, 4th Floor, Franklin Wilkins Building, Kings College London and have the following procedures:

1. Urine samples collected (~0 mins)
2. Finger prick blood test (~10 minutes)
3. Blood pressure (~10 mins)
4. Fasted bloods (~20 mins)
5. Heart rate variability monitor fitted (ECG), to keep on for 48-hours (~10 mins)
6. Ultrasound imaging (~30 mins)
7. STROOP test (~15 mins)
8. Body composition and waist circumference (~10 mins)*
9. Questionnaires (ZOE FFQ) (~15 mins)
10. Dietary consultation (20 mins)***

*Optional break for a snack post measurements.

**Participants will then be instructed to start the dietary protocol after 48 hours after the baseline clinic, when participants' baseline HRV has been recorded.

***Participants will be required to attend a brief consultation with the associate nutritionist on the dietary intervention they have been assigned to. This will cover cooking methods, appropriate food items, and menu card run throughs. It will also provide an opportunity to problem-solve around identified conflicting commitments such as holidays or celebrations, where the participants may not be able to follow the intervention. Standardised advice on eating out will be given to all participants. General healthy eating advice will also be delivered, roughly in line with UK and US dietary guidelines.

5th contact: Dietary assessments for compliance

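### A discarded baseline 24-hour urine also removes that participant's valid midline and endline urines from the change-from-baseline model, at a modest and avoidable cost in precision

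*Combined protocol and SAP*

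**What the plan says.** Under Compliance, section 3.2 gives three signs of an incomplete collection. For the creatinine index the consequence is explicit: "Samples with a creatinine index <0.7 will be discarded as incomplete". Self-reported missed collections and low volumes are also classed as incomplete ("samples with a total volume <400 mL will be marked as incomplete"), but the text does not say what then happens to those samples.

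Section 4.2 sets out the model: "For the outcomes with 3 timepoints (urinary Na, K, Na:K and calystegines" go into a Stata mixed model "with change being the dependent factor, participant ID as random effect, treatment and season as fixed effects, and baseline outcome as a covariate". The statistical row of the synopsis gives the same structure, with "treatment and season as fixed effects, and baseline outcome and BMI as covariates".

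Section 4.2 also states: "We will primarily analyse outcomes on an intention-to-treat basis, analysing participants as randomised". It names no method for missing values.

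On logistics, section 5.4 (Schedule of Treatment) supplies "24-hour urine collection kits (X3) (adherence" to each participant, one for each of the three time points. Participants are told to "start the dietary protocol after 48 hours after the baseline clinic". No repeat baseline collection is described.

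**The concern.** A rule that properly removes one bad sample interacts with a model that needs that sample in order to use any other. When a midline or endline urine is discarded, only its own row is lost. When the baseline is discarded, the participant disappears from the analysis of that outcome, even if both later collections were complete.

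Urinary potassium carries weight here. Section 3.2 says no other biomarker is specific enough to monitor compliance in this design, and section 3.3 makes urine potassium both a compliance measure and a possible stratifier. Potassium is also a central part of the proposed mechanism. Urine is therefore the main objective evidence that the arms differed in what they ate, and valid samples should not be lost through model specification. Losing randomised participants with usable follow-up also sits awkwardly with the stated intention-to-treat analysis.

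A failed baseline may be hard to recover. Section 6.1 has urines analysed in fortnightly batches. If creatinine follows that timetable, which is not stated, the failure would appear only after the diet had begun.

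**Working it through.** **Plan's own figures.** The documents give no incomplete-collection rate and no sample size for the urinary outcomes. The number of completers comes from section 4.1: 80 × 0.85 = 68, or 34 per arm. That sample size (0.468 mmol/L, SD 0.61, alpha 0.025 taken as two-sided) reproduces: the noncentral-t power is 0.8055 at 34 per arm and 0.792 at 33. This point does not affect it.

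**Step 1: why the rows drop.** Let Y0, Y1 and Y2 be the urinary value at baseline, midline and endline. The planned responses are Y1 − Y0 and Y2 − Y0, and Y0 is also a covariate. If Y0 is missing, both responses and the covariate are undefined, so both rows are omitted. If Y1 or Y2 is missing, one row is omitted.

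**Step 2: how many.** Let q be the probability that a sample is discarded, independently at each visit (an assumption), and let N = 68.

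- Participants lost through baseline = N × q
- Valid post-baseline samples = 2N(1 − q)
- Of these, lost with the baseline = 2N(1 − q)q

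| q | Participants lost | Valid later samples | Of these, lost |
|---|---|---|---|
| 5% | 3.4 | 129.2 | 6.5 |
| 10% | 6.8 | 122.4 | 12.2 |
| 20% | 13.6 | 108.8 | 21.8 |

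**Step 3: cost in precision.** Generalised least squares information was computed for 68 participants allocated 1:1, with three visits, equal between-visit correlation of 0.4 to 0.6 (assumed) and random discards, averaged over repeated draws. Two analyses were compared: (a) a valid baseline is required; (b) all valid samples are used, with a common baseline mean. With baseline as a covariate, modelling change or the raw value gives the same treatment effect, so (a) represents the planned model. For the endline effect:

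| q | (a): SE increase over no discards | (b): SE increase over no discards | Variance ratio a/b | SE ratio = square root |
|---|---|---|---|---|
| 5% | 5% | 3% | 1.04–1.05 | 1.02 |
| 10% | 11% | 6–7% | 1.08–1.10 | 1.04–1.05 |
| 20% | 24–25% | 13–14% | 1.18–1.22 | 1.09–1.10 |

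Only the last column is the cost of the model choice. Column (b) is loss that remains for sodium and potassium totals under any model, because an incomplete collection cannot supply a 24-hour total.

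**Step 4: the effect as the plan writes it.** Section 4.2 lists no visit or treatment-by-visit term, so the treatment effect is pooled over midline and endline. For a pooled effect the SE cost is about 1.5–2%, 3–4.5% and 7–10% at q = 5%, 10% and 20%. A separate small simulation (40 runs per rate, correlation 0.5) fitted both mixed models. The SE was 0.188 against 0.180 at 10% (0.188/0.180 = 1.04) and 0.206 against 0.192 at 20% (0.206/0.192 = 1.07).

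Across both effects and both methods the range is about 2%, 3–5% and 7–11%; the top of the range is the endline effect at 20% and correlation 0.4, where the unrounded SE ratio is 1.107.

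**The case against.** The strongest reply is that the effect is small and rests on assumed rates. At 5% discards the SE cost is about 2%. Neither primary outcome is involved, midline compliance monitoring does not use the change model, and the 75% compliance criterion counts checklist days rather than urine. All of that stands and limits the weight of the point. It does not alter the mechanism, which follows from the model as written.

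Four stronger readings are tempting, and the documents do not support them.

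- **That the SE rises by up to 25% because of the model.** Most of that increase comes from discarding incomplete collections, which any analysis of 24-hour totals must also do.
- **That discarding gains nothing in validity.** For sodium and potassium totals it does, because a short collection understates excretion. Only the later loss of valid midline and endline samples has no validity benefit.
- **That discarded and marked samples are deliberately given different treatment.** Section 3.2 puts all three criteria under incompleteness, and the natural reading is a single category. Nothing says marked samples are kept as totals. This is a wording gap.
- **That Na:K needs no complete collection, so its discard is pointless.** Volume does cancel from the ratio, but only for the urine actually collected. Section 3.2 places the potatoes in the evening meal, to be eaten before 8pm, so which voids are missed matters and could matter differently by arm. A partial-day ratio is computable without necessarily representing the 24-hour ratio.

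On status, the synopsis lists urinary potassium, sodium and calystegines as secondary endpoints but not Na:K, which appears in section 4.2. Section 3.3 calls calystegines exploratory and does not say whether they are expressed per 24 hours or per creatinine, so the effect of discarding on that outcome cannot be judged.

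**Conclusion.** The point holds as a modest, avoidable loss of precision. The planned urinary model drops every participant with a discarded baseline urine, including valid later samples, and the plan offers neither imputation nor a repeat collection. At assumed discard rates of 5%, 10% and 20% per visit, about 3, 7 or 14 of 68 completers are lost this way and the SE of the treatment effect is about 2%, 3–5% or 7–11% larger than it need be.

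These figures assume discards that are random and independent across visits, and a between-visit correlation of 0.4 to 0.6. A reader might infer bias in the treatment contrast. None is shown: baseline collections precede the assigned diet, and random discards cost precision only.

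**What to change.** In section 4.2 and the matching synopsis row, make the urinary value at all three visits the response. Include visit, a common baseline mean for both arms, and treatment effects after baseline only (separate for midline and endline, or pooled, as the team intends). Keep the participant random effect and the season term. A missing baseline then no longer removes later valid samples. State that this model is the missing-data approach for the urinary outcomes.

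In section 3.2, keep the exclusion of incomplete collections from 24-hour sodium and potassium totals. State that samples marked incomplete for missed voids or low volume are treated in the same way as those failing the creatinine index. Report Na:K including incomplete collections as a sensitivity analysis only, and state how calystegines are expressed.

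The cost is a few sentences and a different specification of the same Stata mixed command. No new data are needed, because the urine collection form in Appendix 5 already records missed collections, spillages and the 400 mL check. The added assumption is equal baseline means across arms, which randomisation supports.
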